A.8. Summary. Numerous sex differences in behavioral, biological, and clinical correlates of substance use disorders have been identified (Becker et al., 2017), yet there exists a dearth of sex-informed treatment options. Women are more likely to use cannabis for stress reduction (Simons et al., 1998; Terry-McElrath et al., 2009; Cuttler et al., 2016) and demonstrate increased cannabis craving after stress compared to men (Buckner et al., 2011); as such, interventions targeting stress response may have particular salience for cannabis using women. Ovarian hormones have been identified as potential mechanisms of these stress-related disparities (Moran-Santa Maria et al., 2014), and recent clinical trials have begun to examine progesterone's utility as a possible pharmacotherapeutic agent (Evans & Foltin, 2006; Fox et al., 2013; Sofuoglu et al., 2001; 2004; 2011). While progesterone has shown promise as a treatment for women with cocaine and tobacco use disorders, it has not yet been tested in cannabis users. Progesterone may effectively target stress-related craving and cannabis withdrawal symptoms in women, thus reducing relapse rates and improving daily functioning.

B. INNOVATION

The proposed study will test truly novel hypotheses. Specifically, it will build on our previous SCOR work identifying progesterone as an important target in stress-related craving and relapse, while expanding the focus to a previously unstudied addictive disorder. To our knowledge, there are no previous or ongoing studies investigating this promising approach to treating CUD. Additionally, we plan to examine the potentially important effect that progesterone may have on stress, one of the most important contributors to continued cannabis use

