Participants will be provided with a seven-day supply of progesterone or placebo. Randomization to treatment will be done by the MUSC Investigational Drug Service (IDS). Dosing will begin in the evening on study day 1. On study days 2-7 participants will take medication at home in the morning and evening, and on day 8 the final dose will be taken at in the morning prior to completion of the laboratory stress task (described below). Progesterone and matching placebo capsules will be prepared and dispensed by the MUSC IDS. Previous studies (Fox et al., 2013; Sofuoglu et al., 2001; 2011) have used twice daily administration of 200mg progesterone during the early follicular phase to achieve stable levels of progesterone comparable to normal luteal phase levels (2-20 ng/ml). Safety and tolerability of micronized progesterone have been established in numerous studies with nicotine (Sofuoglu et al., 2001; 2011) and cocaine (Evans & Foltin, 2006; Fox et al., 2013; Reed et al., 2011 Sofuoglu et al., 2002; 2004) dependent individuals.

c. Cannabis Abstinence Verification. Cannabis abstinence will be assessed using self-report, saliva drug testing, and cannabinoid levels. Self-report will be collected at study visits using the TLFB as well as collected daily through mobile surveys or “morning reports” completed via mobile electronic device. Participants will be trained to self-administer saliva drug screening (Oratect FDA approved saliva test.). This test is able to detect THC in saliva for up to 14 hours. Participants will be instructed to complete two saliva drug tests daily using the RedCap video upload procedure described below under *Medication Adherence/Drug Test Monitoring*. A test will be completed in the office on Day 1 so patients can practice the procedure. Cannabinoid levels will also be assessed using urine toxicology collected on Study Days 8 and 22. Creatinine-corrected cannabinoid levels will be compared from Day 1 to Day 8 to confirm abstinence during the study period. Our group has recently published on the need for utilization of multiple methods to determine cannabis abstinence (Baker et al., in press). Contingency management (monetary compensation) procedures will be incorporated to promote abstinence (described below).

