Following the initial 7-day active exogenous progesterone treatment period, participants will return for a laboratory-based stressor a session. The primary study outcomes of interest in Aim 2 are the differential craving, stress and anxiety responses of progesterone- vs. placebo-treated participants in response to the psychosocial stressor (TSST). Hypothesis 1: Compared to placebo, progesterone will attenuate stress cue reactivity during a human laboratory stress paradigm among women but not men with CUD. Immediately prior to and following the TSST (baseline, +0, +5, +30, and +60 minutes), self-reported measures of stress and craving will be collected. To assess the effect of exogenous progesterone administration on stress and craving response to the TSST, linear mixed effects models will be developed to assess differential treatment responses over time. The primary independent variable of interest will be randomized treatment assignment (progesterone vs. placebo). In addition to overall treatment differences, least squares means and associated standard errors will be used for post-hoc

comparisons between treatment groups at each post-cue time point. Additionally, sex will be added to the model and differential effect of progesterone will be assessed using an interaction term. When significant, stratified treatment effects will be compared and presented across females and males.

Aim 3: Evaluate stress, sex, and endogenous progesterone influences on cannabis craving and use.

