Endogenous progesterone levels (via saliva samples) will be obtained daily for two weeks following the completion of the active medication portion of the study. Daily progesterone levels will be assessed for associations with stress and craving responses to stress vs. neutral CREMA cues. *Hypothesis 1: Among women, higher daily levels or increasing endogenous progesterone will be associated with decreased cannabis use.* To evaluate this hypothesis, a multilevel generalized linear mixed effects models with repeated measures (GLMMs) will be developed using CREMA session response data from the 2-week follow up period. Statistical models will include day and subject level data, measured longitudinally. Daily salivary progesterone levels will be included as the primary independent predictor cannabis use. Relevant interactions will be assessed in all models. Additionally, increases in progesterone during the early luteal phase of each female participant's cycle will be evaluated; models will include dynamic changes in progesterone (between day rates of change) as a predictor of attenuated cannabis use. *Exploratory Hypothesis 2: High stress will be associated with cannabis craving and return to cannabis use in women more than men.* Time from the laboratory session to return to cannabis use (latency, in days) will be computed for all study participants. Kaplan-Meier estimates and log-rank tests will be used to assess initial relationships between measures of stress reactivity during the TSST (e.g., subjective stress, anxiety, BP, HR, cortisol) and relapse/latency while Cox proportional hazards models will be developed to assess the differential latency to use across sex for each stress reactivity measure during the TSST (using an appropriate interaction term; e.g. Peak TSST stress response x sex). Additionally, daily stress and craving responses to CREMA picture cues will serve as time-dependent covariates in latency models to assess the influence of recent stress and craving responses on relapse/latency.

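### The exploratory Aim 3 Cox models use a TSST response measured on study drug but name no term for randomised arm, which can bias the stress-by-sex estimate

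*Combined protocol and SAP*

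**What the plan says.** Section C.2.c.3, on study medication, states that "on day 8 the final dose will be taken at in the morning prior to completion of the laboratory stress task". The Trier Social Stress Test (TSST) response is therefore a post-randomisation measure taken on drug. Aim 2 in section C.2.d.1 hypothesises that "progesterone will attenuate stress cue reactivity during a human laboratory stress paradigm among women but not men with CUD", and makes randomised assignment its main independent variable.

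Aim 3 then uses the same response as a predictor. The relevant part opens with "Exploratory Hypothesis 2: High stress will be associated with cannabis craving and return to cannabis use in women more than men". Latency is counted in days from the laboratory session. Kaplan-Meier and log-rank analyses come first, and then "Cox proportional hazards models will be developed to assess the differential latency to use across sex for each stress reactivity measure during the TSST", with the sex difference tested "using an appropriate interaction term; e.g. Peak TSST stress response x sex". For Hypothesis 1, in women, the text says "Daily salivary progesterone levels will be included as the primary independent predictor cannabis use" and adds "Relevant interactions will be assessed in all models".

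Neither Aim 3 model names randomised arm, and no analysis in the documents compares cannabis use or latency between the arms. Section C.2.d.1 places the complete analysis plan in the Biostatistics Resource Core, which is not among the documents.

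**The concern.** Follow-up is not an untreated period for everyone: about half the participants have just had a week of progesterone. By the plan's own hypotheses, arm moves the predictor, and by a different amount in each sex. Section A.8 also expects an effect on the outcome: "Progesterone may effectively target stress-related craving and cannabis withdrawal symptoms in women, thus reducing relapse rates and improving daily functioning". A variable that shifts the predictor differently in women and men, and may shift the outcome, is a potential confounder of the very term that Exploratory Hypothesis 2 is about.

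There is a second route. Return to use happens off drug. If a person's usual reactivity drives it, the Day 8 score of a treated woman is a displaced version of the relevant quantity, and the pooled slope is diluted.

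At stake is a reported sex difference in stress sensitivity that is partly a treatment effect, or a real difference that is understated. In addition, the one contrast on return to use that randomisation supports is not described.

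Hypothesis 1 has a related but different weakness. Its planning effect (section C.2.d.3) comes from untreated women. Aim 3 treats follow-up progesterone as endogenous and states no washout, although section C.2.e gives carry-over as a reason against a crossover.

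**Working it through.** **The plan's own figure.** The documents give no power, event count or hazard ratio for the Cox analysis. The only Aim 3 figure is 80% power for Hypothesis 1 (C.2.d.3: 62 women, 14 days, autocorrelation 0.9, slope 0.32, SD 1.0). With exchangeable correlation, effective n = 62 × 14 / (1 + 13 × 0.9) = 868 / 12.7 = 68.35. Power = Φ(0.32 / √(1 − 0.32²) × √68.35 − 1.96) = Φ(0.83) = 79.7%. It reproduces, so the point rests on no arithmetic error.

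**Inputs for the Cox check.**
- From the documents: 70 women and 90 men randomised, 10% attrition to Day 8, so 70 × 0.9 = 63 and 90 × 0.9 = 81; 14 days of follow-up; planning shifts in stress response of 0.71 SD downward in women and 0.2 SD upward in men (C.2.d.3, used here as a stand-in for the TSST).
- Assumed: equal arms; stress log hazard ratio 0.3 per SD in both sexes, so the true interaction is zero; 65% to 80% returning to use by the end; direct arm hazard ratio (HR) varied from 1.0 to 0.4.

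**Route 1: arm affects use other than through the measured response.** To first order, omitting arm moves a within-sex slope by ln(HR) × (δ/4) / (1 + δ²/4), where δ is the arm shift in SD.
- Women, δ = −0.71: −0.1775 / 1.126 = −0.158.
- Men, δ = +0.2: 0.05 / 1.01 = +0.050.
- HR 0.6 in women only: −0.511 × −0.158 = +0.08. HR 0.6 in both sexes: +0.08 − (−0.511 × 0.050) = +0.08 + 0.03 = +0.11.

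Simulation (1,500 runs) agrees. Entries are the false interaction and the rejection rate of a 5% test:

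| Direct arm HR | Formula | Arm omitted | Arm and arm × sex added |
|---|---|---|---|
| 1.0 | 0 | −0.02 (5.5%) | −0.02 (5.7%) |
| 0.8, women only | +0.04 | +0.04 (5.3%) | +0.01 (5.0%) |
| 0.6, women only | +0.08 | +0.08 (7.6%) | 0.00 (4.8%) |
| 0.4, women only | +0.14 | +0.13 (8.8%) | 0.00 (4.6%) |
| 0.6, both sexes | +0.11 | +0.12 (10.0%) | +0.01 (5.7%) |
| 0.4, both sexes | +0.19 | +0.20 (14.9%) | +0.01 (5.5%) |

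The Monte Carlo error of a 5% rate is √(0.05 × 0.95 / 1500) = 0.6 percentage points, so 5.3% cannot be told from 5%. With a women-only effect, an arm main effect alone leaves +0.04 of the +0.08 at HR 0.6, about half. If treated women return sooner, the sign reverses: in a separate run with no stress effect and an arm log hazard ratio of +0.7 in women, the interaction was about −0.12.

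**Route 2: usual off-drug reactivity drives use.** Take true slopes of 0.5 in women and 0.2 in men, so a true interaction of 0.30. Each slope on the Day 8 score is divided by 1 + δ²/4: 0.5 / 1.126 = 0.444 and 0.2 / 1.01 = 0.198, a difference of 0.25. Simulation with 63 women and 63 men gave 0.24, and 0.30 with the arm terms. Power was 24% without them and 30% with them.

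**Hypothesis 1** (true slope zero, 300 runs, assumed cycle shape). A constant arm effect of −0.5 SD on use left the daily-progesterone slope at 0.00 with or without arm, because the estimate is almost wholly within-person. The same effect decaying over 3 days gave +0.045 (97% rejection). Adding arm changed nothing; adding day and arm × day cut it to +0.012 (13%). With residual drug on the first two days as well, the bias was −0.016 (27%), and −0.015 (23%) with arm × day.

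**The case against.** The strongest reply is that Aims 1 and 2 concern only the effect of arm on stress, craving and withdrawal. If progesterone changes return to use purely by changing the measured stress response, the Cox model already contains the path and nothing is lost; the first row of the table shows this. The rationale in section A.8 reads largely as mediation. So a reader might infer that the Aim 3 estimate must be biased if Aims 1 and 2 succeed, and the documents do not support that. What stands is narrower. A.8 names withdrawal as well as stress-related craving, the TSST score need not capture all of either, and the second route needs no lasting drug effect on relapse.

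A reader might also infer that the Hypothesis 1 model is confounded for the same reason. It is not: a constant arm effect barely touches a within-person slope. The exposure there is to decaying carry-over and residual exogenous hormone, and an arm main effect does not cure it.

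Third, a reader might infer that the analysis excludes arm. The documents do not show this. The complete plan is elsewhere, subject-level data could include arm, and the general sentence on interactions could be read to cover it. But arm is named for Aim 2 and not for Aim 3.

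Fourth, the analysis is exploratory and its hypothesis is one of association, so no primary conclusion depends on it. That is correct and limits the weight of the point. Comparing latency between arms does go beyond the stated scope of Aim 3. It is recommended because the study title and A.8 both raise progesterone's effect on use or relapse.

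**Conclusion.** The point holds as a conditional one. The TSST predictor is measured on drug, arm is expected to shift it differently by sex, and the Cox models described do not name arm. The stress-by-sex estimate can therefore be biased, but is not certain to be.

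The false interaction runs from about +0.04 (direct HR 0.8, women only) to +0.20 (HR 0.4, both sexes), with type I error from about 5% to 15%. It is nil if arm acts only through the measured response. If off-drug reactivity drives use, a true 0.30 is estimated at about 0.25. The direct arm hazard ratios, stress effect and relapse rate are assumptions; the documents give none of them. At an HR of 0.8 the practical effect is small.

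For Hypothesis 1 the concern is limited to carry-over that fades and drug still present in the first follow-up days; its size depends on an assumed effect, decay and cycle shape.

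**What to change.** 1. Add randomised arm and arm × sex to the Cox models of Exploratory Hypothesis 2. Arm alone is not enough if the effect is confined to women. Give a placebo-only estimate as a sensitivity analysis; with equal arms it rests on roughly half of the 63 women and 81 men, so it will be imprecise.
2. Report arm and arm × sex effects on latency from a Cox model without the TSST term, as the randomised comparison for return to use. The TSST term must be left out because it lies after randomisation. Latency starts on Day 8, so state that this comparison covers those who reach the laboratory session and report losses by arm.
3. For Hypothesis 1, include arm, day and arm × day, with a sensitivity analysis in placebo women or without the first follow-up days. The second option matters because arm × day did little against residual drug.
4. If the Biostatistics Resource Core plan already has these terms, one sentence of cross-reference in section C.2.d.1 is enough.

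The cost is wording, a few model terms and a slightly wider interval if there is no carry-over. For Hypothesis 1, adding an arm term leaves power at 79.7% if arm and progesterone are uncorrelated, 78.1% at a correlation of 0.2 and 75.9% at 0.3, from Φ(0.32 / √(1 − 0.32²) × √68.35 × √(1 − r²) − 1.96).

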C.2.d.3. Power and Sample Size (complete sample size estimation is provided in Biostatistics Resource Core). In the proposed study, cue response and withdrawal data will be tested using GLMMs (assuming a Gaussian distribution) and the study will be powered to sufficiently address the smallest effect sizes determined to be clinically meaningful for the study hypothesis. Fox and colleagues (2013) examined exogenous progesterone and placebo administration on cue response in 42 cocaine dependent participants. Results indicated that female participants receiving placebo experienced larger negative emotion scores in response to stress-related cues than male participants on placebo ($\Delta=4.7$; $SD_P=3.4$; between sex Cohen's $d > 1.0$, $p < 0.01$). Fox and colleagues also found that administration of exogenous progesterone reduced stress-cue related negative emotions significantly in women ($\Delta=2.4$; $SD_P=3.4$, $d=0.71$) but not in men ($\Delta=-0.7$; $SD_P=3.3$ $d=-0.2$; treatment x sex interaction $\Delta=3.1$; $SD_P=4.7$, $d=0.67$). Assuming a similar response profile between treatment assignments and sex as above, a sample size of 64 participants (32 women, 32 men to each treatment assignment) randomized to the progesterone vs. placebo groups would guarantee 80% power with a type 1 error rate of 5% to detect the least effect size of $d=0.67$ in the stress reduction treatment x sex interaction (total $n=128$) during the 7-day, active treatment CREMA assessment period. Although the proposed study is of relatively short duration, we do anticipate 10% attrition between randomization and the end of the 1-week active treatment period and laboratory session. Thus, inflating the necessary sample size to 70 participants (35 men and 35 women), a total of $n=140$ randomized participants will be needed. Due to app issues at the beginning of the study, some initial data is unusable, so we will randomize 90 men. Additionally, data from our recently completed SCOR project, which examined daily salivary progesterone levels and cigarette smoking behavior for 14 consecutive days in untreated female participants, indicated that increased levels of daily progesterone within participant was associated with decreased cigarettes smoked per day ($\beta=-0.32$; $SE=0.14$; $p < 0.05$). To detect a similar correlation ($\beta=\pm 0.32$; $SD=1.0$) between daily progesterone levels and associated daily use metrics in the proposed study, the randomized sample of 70 women (62 with available follow up data), with 14 days of follow up use data, and with an autocorrelation of 0.9, would provide 80% power. The proposed sample size of **n=160** randomized

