
participants would provide 80% power or better to detect the proposed between sex and treatment comparisons noted in the primary study aims.

C.2.e. Design Considerations. **i) Choice of between vs. within participant design.** We considered implementation of a within-subject crossover design but opted instead for a between-subjects parallel-group comparison study for multiple reasons. Most notably, a within-subjects approach risks potential carryover effects between conditions, as well as potential dampening of cue reactivity and participant response fatigue over extended periods of testing across conditions. Additionally, withdrawal symptoms may not present consistently or reliably across multiple conditions in series without a lengthy/sustained return to *ad libitum* cannabis use between conditions. **ii) Choice of administration of progesterone during cannabis withdrawal.** Cannabis withdrawal is characterized by increased anxiety, irritability, craving, and physiological symptoms, which peak within the first 2-3 days of abstinence (Budhey et al., 2008). Acute cannabis withdrawal is therefore an ideal period to investigate potential therapeutic effects of progesterone on stress cue reactivity and craving. **iii) Focus on progesterone.** The proposed study focuses on progesterone because evidence suggests that estradiol may enhance drug reinforcement and cue-reactivity. In preclinical studies, estradiol has been shown to increase dopamine release in the ventral striatum in response to nicotine administration (Thompson et al., 1994), and facilitate methamphetamine-induced conditioned place preference (Chen et al., 2003) and cocaine self-administration (Lynch, 2008; Lynch et al., 2001). Clinical research on menstrual cycle phase has demonstrated greater smoking cue-elicited neural activity and craving response during the follicular phase (where estradiol dominates) compared to the luteal phase (Franklin et al., 2015; Mendrek et al., 2014). Likewise, women with a higher estradiol to progesterone ratio took more cigarette puffs and smoked more of a cigarette in a smoking topography study (Schiller et al., 2012). Furthermore, compared to men, women smokers in the follicular phase showed increased stress response and arousal while women in the luteal phase showed increased craving ([name] et al., 2015b). Together, evidence suggests that estradiol enhances drug reinforcement and cue-reactivity, and hence may contribute to the more deleterious outcomes observed in substance using women. Accordingly, we have focused this project on expanding knowledge about the treatment potential of progesterone (as characterized in the Significance above) by examining its effects on stress reactivity and substance use in persons with CUD. **iv) Male comparison group.** Apart from the obvious relevance of a male comparison group in studies of sex differences, there are empirical grounds for including men in proposed study. Sofuo glu et al., (2004) found that 2 oral doses of 200 mg progesterone significantly dampened cardiovascular responsiveness (diastolic BP) to iv cocaine in male, not female, cocaine users. Likewise, Fox et al., (2014) reported that exogenous progesterone vs. placebo attenuated cue-induced cocaine craving and cortisol responses in both men and women, suggesting that progesterone may also have some treatment potential for male cocaine users. Based on these and similar findings (Childs et al., 2010), we believe the proposed study's inclusion of both women and men with CUD will optimize our ability to identify therapeutic effects of progesterone that are either unique to one sex, or present in both.

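### C.2.d.3: the printed inputs for the treatment-by-sex interaction give about 74–76% power at 32 per cell, not 80%, unless an unstated assumption is added

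*Combined protocol and SAP*

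**What the plan says.** All the inputs are in C.2.d.3 and come from a cited 42-person study of progesterone in cocaine dependence. The effect on stress-cue negative emotion was significant in women: "stress-cue related negative emotions significantly in women ($\Delta=2.4$; $SD_P=3.4$, $d=0.71". It was absent in men: "but not in men ($\Delta=-0.7$; $SD_P=3.3$ $d=-0.2". The two are combined as "treatment x sex interaction $\Delta=3.1$; $SD_P=4.7$, $d=0.67".

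The base sample size is "a sample size of 64 participants (32 women, 32 men to each treatment assignment) randomized to the progesterone vs. placebo groups", which the plan says "would guarantee 80% power with a type 1 error rate of 5% to detect the least effect size of $d=0.67" for the interaction, with 128 in total. The count then rises to 140 for 10% attrition, and to 160 (90 men, 70 women) because some early app data are unusable. The section ends by saying that the 160 randomized "participants would provide 80% power or better to detect the proposed between sex and treatment comparisons noted in the primary study aims".

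The error rate appears only as "with a type 1 error rate of 5" per cent, without saying whether the test is one- or two-sided. No number of sessions, within-person correlation or covariate gain is given for the interaction calculation. The section heading refers the reader to the Biostatistics Resource Core for the complete estimation.

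**The concern.** The section prints an effect, an SD, a cell size, an error rate and a power. The first four should produce the fifth, and under the usual convention they do not.

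The interaction carries weight. It is the contrast on which the trial is sized, and both Aim 1 hypotheses in C.2.d.1 are framed as women versus men. If it comes out null, readers will judge that result against a stated 1-in-5 chance of missing a true effect of this size. On the printed inputs the chance is nearer 1 in 4. The word *guarantee* adds to the problem, because any power figure is conditional on an assumed effect, and this one comes from a small study in a different population.

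**Working it through.** **Inputs (C.2.d.3).** Difference in women 2.4, SD 3.4; difference in men −0.7, SD 3.3; interaction 2.4 − (−0.7) = 3.1; stated SD 4.7; stated d = 0.67; 32 per sex-by-treatment cell. **Assumed, because not stated:** two-sided 5% test and one summary value per person.

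**Scale of d.** √(3.4² + 3.3²) = 4.74, so the stated 4.7 combines the two within-sex SDs. The variance of the interaction estimate is 2(3.4²)/32 + 2(3.3²)/32, so SE = 1.185, which equals 4.74 × √(2/32). The contrast therefore behaves like a two-group comparison with 32 per group, and its noncentrality is d × √(32/2) = 4d. The printed figures also give slightly different values of d: 3.1/4.7 = 0.660 and 3.1/4.74 = 0.654, against the stated 0.67. All three were run.

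**Power at 32 per cell, two-sided 5%.**

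| d used | Noncentrality | Noncentral t, 124 df | Normal |
|---|---|---|---|
| 0.67 (as stated) | 2.68 | 75.8% | 76.4% |
| 3.1/4.7 = 0.660 | 2.64 | 74.5% | 75.1% |
| 3.1/4.74 = 0.654 | 2.62 | 73.8% | 74.4% |

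The stated 80% is not reproduced; the shortfall is 3.6 to 6.2 points.

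**What 80% would need.**
- At d = 0.67, normal approximation: 2(1.960 + 0.842)²/0.67² = 34.97, so 35 per cell (140 completers). By noncentral t, 35 gives 79.5% and 36 gives 80.6%, so 36 per cell (144).
- At 3.1/4.7: 37 per cell (148).
- With 32 per cell: d = 0.706 by t, or 2.80/4 = 0.700 by the normal approximation.

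**Assumptions that could close the gap.**
- *One-sided 5%:* 83–85% over the three values of d.
- *Repeated sessions:* one stress picture a day from Day 2 (C.2.c.3, part e) gives six on Days 2–7. If the SDs refer to one session, averaging multiplies the variance by (1 + 5 × ICC)/6. At ICC 0.8 the factor is 0.833, and power is 83% at d = 0.67 and 81% at 3.1/4.74. At ICC 0.9 the factor is 0.917, and power is 79% and 77%.
- *Pre-cue covariate:* the variance is multiplied by 1 − r². At r = 0.35, power is 81% at d = 0.67 and 79% at 3.1/4.74.

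**The 160 randomized (two-sided, one value per person, by t).** After 10% attrition, women are 35 × 0.9 = 31.5 per cell. If every retained man is usable, men are 45 × 0.9 = 40.5 per cell. SE in units of the interaction SD is √(1/31.5 + 1/40.5) = 0.2376, and power is 78–80%. If the added men only replace unusable data, leaving 31.5 per cell, power is 73–75%.

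**The case against.** The strongest reply is that 74–76% describes a simpler analysis than the trial will run. C.2.d.3 says cue response will be tested with mixed models. C.2.d.1 specifies repeated measures over the treatment week, with pre-cue ratings as a time-varying covariate. The hypotheses there are also directional. A one-sided test, an ICC of about 0.8, or a covariate correlation of about 0.35 at the stated d would each bring power to 80% or above. The inputs may be written out in the Biostatistics Resource Core, which cannot be checked here.

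Much of this stands. It rules out saying that 128 is too small for the planned analysis. It does not rescue the sentence as written, because the section claims none of these gains for the interaction. The same section does state its repeated-measures inputs for the daily progesterone calculation: 14 days and an autocorrelation of 0.9. The benefit is also not automatic, since an ICC of 0.9 leaves power just under 80%.

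A reader might also infer that 32 was taken from another calculation. The women-only effect (d = 0.71, 32 versus 32) does give 79.8% by t and 81.1% by the normal approximation. The documents do not say where 32 came from, so this remains a guess and the point does not use it.

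**Conclusion.** The stated 80% does not follow from the inputs printed beside it. With a two-sided 5% test and one summary value per person, power at 32 per cell is about 74–76%, a miss rate of 24–26% instead of 20%. The gap is small and depends on those two assumptions, which are conventional but are not the plan's own words. This is a modest correction to a sizing statement.

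Two stronger readings are not supported. One is that the trial is underpowered and must enrol more: plausible repeated-measures or covariate gains could cover the gap, and the document that might state them is not available. The other is that the closing sentence on 160 randomized is wrong. That sentence concerns a different number, and its power is 78–80% or 73–75% depending on how many of the added men have usable data, which the plan does not report.

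**What to change.** In C.2.d.3, delete *guarantee* and do one of two things:

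- Restate the claim along these lines: 128 completers give about 75% power (two-sided 5%, one summary value per person) for the treatment-by-sex interaction at d = 0.67, and 80% at d of about 0.71.
- Keep 80%, but state the sidedness, the number of on-treatment stress sessions, the ICC and the pre-cue covariate correlation that produce it, and show the result. If these are already in the Biostatistics Resource Core, carry them into this section.

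Then recompute the closing sentence on 160 randomized under the same assumptions, using the expected number of men with usable data, and restate it only if the result is below 80%.

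The cost is protocol wording and a short recalculation. Enrolment, design and analysis do not change. Under the first option the stated power becomes slightly less favourable.
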